5. OBJECTIVES

5.1 Primary Objective

To evaluate the sensitivity, specificity, positive and negative predictive value of metabolomic biomarkers in exhaled breath samples to identify acute breathlessness, defined as one or more of (i) patient defiend acute breathlessness and/or a (ii) 1 unit increase in Extended Medical Research Council breathlessness score (eMRC)

Page 14 of 46

- Recruitment in to the acute breathlessness group will be according to the following defined primary diagnoses in the discovery phase as defined by the treating physician:
 - (i) Acute Heart failure (n=55-100), (ii) Community acquired pneumonia (n=55-100), (iii) Adult exacerbations of asthma and COPD (n=110-200) and (iv) paediatric exacerbations of acute childhood wheeze and/or confirmed asthma (n=50-100). Additionally age/home environment matched adult/spouse/sibling/parent control subjects (n=55-150 adults/50 children).

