7 TRIAL PARTICIPANTS

7.1 Overall Description of Trial Participants

Each site will recruit patients with acute breathlessness. Final confirmation of the primary indicator diagnosis is usually available at discharge (following visit 1b) and after further diagnostics at the stable state follow up clinic (at visit 2). The final primary indicator diagnosis and additional comorbidities will be recorded at initial senior clinical review, discharge and at follow up. The indicator diagnosis will be used to define the number of patients recruited within each disease stratum.

The study will have two distinct phases:

Phase 1: Discovery of novel breath metabolomic biomarkers.

Phase 2: Replication and validation of selected biomarkers in Phase 1.

Planned recruitment to meet the primary, secondary and exploratory study endpoints is outlined below.

- (i) Acute Heart failure (n=55-100 Phase 1, n=55-100 phase 2)
- (ii) Adult community acquired pneumonia (n=55-100 Phase 1, n=55-10 Phase 2). This condition will be defined as new radiological consolidation responsive to treatment according to the British Thoracic Society (BTS) community acquired pneumonia guidelines.
- (iii) Adult exacerbations of airway diseases asthma and COPD (n=110-200 Phase 1, n=110-200 Phase 2). This condition will be defined as a clinician diagnosis with subsequent or historical evidence of objective diagnostic criteria according to national and international guidelines.
- (iv) Paediatric exacerbations of acute childhood wheeze and/or confirmed asthma (n=55-100 Phase 1, n=25-50 Phase 2).

This condition will be defined as a clinician diagnosis and for childhood wheeze/asthma subsequent or historical evidence of objective diagnostic criteria according to national and international guidelines.

(v) Age/environment matched Adult/spousal/parental/ sibling volunteers (n=55-150 adults/50 children) discovery phase, (n=55-75 adult/25 children)

replication phase) with no evidence or history of the indicator disease being evaluated in their spouse/sibling/child.

(vi) Stable state participants with a confirmed diagnosis of asthma, COPD or heart failure that have not had and exacerbation of their disease within the preceding 6 weeks (n=200 (100 in each phase)).

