10. STATISTICS

participants.

10.1 Description of Statistical Methods (Detailed statistical anad analytical methods are outlined in the MRC-EMBER data analysis plan).

Primary Analysis

For the primary analysis the outcome is a nominal variable with levels (1) Acute breathlessness (2) Recovery form acute breathlessness. The relationship between the primary outcome and the metabolomics biomarkers in exhaled breath sample will be modelled using multinomial logistic regression. Acute

Page 32 of 46

breathlessness will be defined as one or more of (i) patient defined acute breathlessness and/or a (ii) 1 unit increase in Extended Medical Research Council breathlessness score (eMRC). In addition to metabolomics markers the following independent variables will be included in the model: age, sex, standard acute care pathology markers blood eosinophils, BNP, CRP, Troponin-I, canonical VOCs extracted from breath analysis and where relevant validated co morbidity scores (e.g. Charlson comorbidity score).

Adjudication

All acute/healthy adult patients' notes will be sequentially divided. These will then be reviewed and independently adjudicated by two independent respiratory consultants, blinded to admission bloods and diagnosis. The panel will independantly decide the primary diagnosis as well as mark their level of certainty on a 100 mm VAS scale. The panel member will then be able to review imaging, ECGs, and ABGs but not blood results. Results will be both -validated by separate panel member to ensure agreement using Bland-Altman and Correlations and within rater agreement will be assessed by replicate analysis of at least 20 cases 4 weeks apart.

Binary logistic regressions will be utilised to assess associations between VOCs and acute disease. ROC curves will be produced for individual predictors in the primary analysis. Additional techniques for multi variate analysis including but not limited to cluster analysis, structural equation modelling and topological data analyses will be applied where relevant. Tables of descriptive statistics will be compiled for all key variables. All analysis will be performed using SAS 9.4 http://www.r-project.org/.

Secondary Analysis

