21.3 Closed formula for sensitivity and specificity of disease biomarkers

Page 44 of 46

The closed formulae in Tilaki-Hajjan *et al*, Journal of Biomedical Informatics 48(2014), 193-2014, were also utilised to understand the power that the samples size above would provide with respect to biomarker sensitivity and specificity.

The following assumptions were made:

- That a sensitivity of 80 % with a precision (d) of between 5-8% would provide a useful biomarker capable of 'ruling out' an acute class. The same target was applied to specificity.
- We assume a prevalence of acute breathlessness of 80% as the MRC EMBER campaign
 uses acute breathlessness as the initial stratification tool for recruitment and 1:5 patients
 recruited will be non-breathless healthy controls. We aim to balance group sizes across
 classes equally.
- A type 1 error rate of 0.05 and power of 95% CI level, 90% CI level
- Note for a prevalence ≥ 50% Nspec ≥ Nsens is always the case, so N_{spec} is the number we need to consider.

95% CI, precision ± 5%

 N_{sens} = 1.96² x 0.8 x 0.2 / 0.05² x 0.8 = 307

 N_{spec} = 1.96² x 0.8 x 0.2 / 0.05² x 0.2 = 1,230

90% CI, precision ± 5%

 N_{sens} = 1.64² x 0.8 x 0.2 / 0.05² x 0.8 = 215

 N_{spec} = 1.64² x 0.8 x 0.2 / 0.05² x 0.2 = 861

To obtain n near 550, increase the maximum marginal error d (i.e. decrease the precision)

95% CI, precision ± 8%, Prevalence = 80%, Sensitivity and Specificity=80 %

 $N_{sens} = 120$

 $N_{\text{spec}} = 480$

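### PPV and NPV are listed as primary measures, but recruitment quotas or the visit schedule set the acute share, so raw sample values cannot be read as clinical predictive values

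*Protocol*

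**What the plan says.** Section 5.1, repeated in the synopsis, puts four accuracy measures side by side in the primary objective: "To evaluate the sensitivity, specificity, positive and negative predictive value of metabolomic biomarkers" in exhaled breath, for identifying acute breathlessness.

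The same section then fixes who is recruited. It states "Recruitment in to the acute breathlessness group will be according to the following defined primary diagnoses in the discovery phase", and gives numbers for the adult groups ("i) Acute Heart failure (n=55-100), (ii) Community acquired pneumonia (n=55-100), (iii) Adult exacerbations of asthma and COPD (n=110-200") and for "control subjects (n=55-150 adults/50 children". Section 7.1 adds: "The indicator diagnosis will be used to define the number of patients recruited within each disease stratum". Under section 7.2 (iv), acute breathlessness is an entry criterion for patients and is waived for healthy subjects and matched controls. Sections 21.4 and 21.5 set equal adult classes: 110 each for asthma, COPD, heart failure, pneumonia and healthy volunteers over the two phases.

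Section 21.3 sizes the study for sensitivity and specificity. There "We assume a prevalence of acute breathlessness of 80" per cent is the protocol's input, and the reason given is the design itself: one in five "recruited will be non-breathless healthy controls. We aim to balance group sizes across" classes.

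Section 10.1 describes a different contrast for the primary analysis: "the outcome is a nominal variable with levels (1) Acute breathlessness (2) Recovery form acute breathlessness".

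The protocol gives no clinical prevalence, no recalculation of PPV or NPV to one, and no precision target for either.

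**The concern.** Sensitivity and specificity are each conditional on true status, so they can be estimated when the numbers with and without the condition are chosen in advance. PPV and NPV are conditional on the test result and also depend on the share of tested people who have the condition. In this study the protocol chooses that share: quotas set it for acute versus healthy, and the visit schedule sets it for acute versus recovery.

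If PPV and NPV are taken from the sample as the objective reads, two of the four named primary measures would move with recruitment and with the comparator even if the test did not change. Section 21.3 looks for a biomarker that can rule out an acute class. A reader interested in ruling out will look first at NPV, and the calculations below show that NPV shifts more than PPV across the permitted mixes.

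**Working it through.** **Inputs from the protocol**
- Target sensitivity (Se) and specificity (Sp): 80% each (section 21.3).
- Planned adult totals: 4 × 110 = 440 acute and 110 healthy (sections 21.4 and 21.5).
- Adult discovery ranges (section 5.1): acute 55 + 55 + 110 = 220 up to 100 + 100 + 200 = 400; adult controls 55 to 150.

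**Step 1: reproduce the protocol's own figures.** With prevalence 0.8, N_sens = z² × Se(1 − Se) / (d² × 0.8) and N_spec = z² × Sp(1 − Sp) / (d² × 0.2).
- 95% CI, ±5%: 3.8416 × 0.16 / (0.0025 × 0.8) = 307.3, and 3.8416 × 0.16 / (0.0025 × 0.2) = 1,229.3. Stated: 307 and 1,230.
- 90% CI, ±5%: 2.6896 × 0.16 / 0.002 = 215.2, and 2.6896 × 0.16 / 0.0005 = 860.7. Stated: 215 and 861.
- 95% CI, ±8%: 0.614656 / (0.0064 × 0.8) = 120.1, and 0.614656 / (0.0064 × 0.2) = 480.2. Stated: 120 and 480.

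All six agree, apart from rounding. In these formulas 0.8 is the fraction of the sample that is acute, and that is the correct quantity for sizing.

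**Step 2: predictive values for one unchanged test.** With p the acute share,

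PPV = Se·p / [Se·p + (1 − Sp)(1 − p)] and NPV = Sp(1 − p) / [Sp(1 − p) + (1 − Se)p].

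In counts, with Se = Sp = 0.8:
- 440 acute, 110 healthy (p = 80%): PPV = 352 / (352 + 22) = 94.1%; NPV = 88 / (88 + 88) = 50.0%.
- 220 acute, 150 controls (p = 59.5%): PPV = 176 / (176 + 30) = 85.4%; NPV = 120 / (120 + 44) = 73.2%.
- 400 acute, 55 controls (p = 87.9%): PPV = 320 / (320 + 11) = 96.7%; NPV = 44 / (44 + 80) = 35.5%.

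The last two mixes lie within section 5.1's permitted adult discovery ranges and need no outside assumption.

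**Step 3: the acute-versus-recovery contrast of section 10.1.** The protocol does not say what share of patients will give a recovery sample. Assuming one acute sample per patient and a fraction m with one recovery sample, p = 1 / (1 + m):

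| m (assumed) | p | PPV | NPV |
|---|---|---|---|
| 1.0 | 50.0% | 80.0% | 80.0% |
| 0.8 | 55.6% | 83.3% | 76.2% |
| 0.7 | 58.8% | 85.1% | 73.7% |

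**Step 4: reference points.** At the planned 80% mix, a test with no information (for example Se = Sp = 0.5) already has PPV 80% and NPV 20%. At an assumed prevalence of 20%, which the protocol does not give, the 80%/80% test has PPV 50.0% and NPV 94.1%.

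**The case against.** The strongest reply is that naming PPV and NPV in an objective is not itself an error. The protocol nowhere says that they will be raw sample proportions or be offered as clinical values. Section 10.1 refers to a separate data analysis plan, which is not shown and could specify a prevalence. Sensitivity and specificity come first in the objective, are the only accuracy measures sized in section 21.3 and the only ones for which section 21.4 claims power. Section 10.2 calls the study exploratory.

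Much of this stands. No sample size or stated decision depends on PPV or NPV, and a reader given sensitivity and specificity can compute predictive values at any prevalence. It does not remove the point. The objective gives PPV and NPV equal primary standing in a design that cannot supply them as clinical quantities without outside information, and the protocol neither supplies that information nor limits how the values may be read.

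Three stronger readings are tempting, and the documents do not support them:
- A reader might infer that the predictive values would reflect only the design and say nothing about the test. They depend on both.
- A reader might infer that the 80% in section 21.3 is a mistaken clinical prevalence, or that the sample size is wrong because of it. The protocol says openly that it comes from recruitment, and it is used properly, as a sample fraction.
- A reader might infer that Bayes' rule repairs everything. It assumes that sensitivity and specificity carry over to the clinic, which comparisons with healthy volunteers or recovered patients do not establish. It also leaves open that section 10.1 compares acute with recovery while section 21.3 compares acute with healthy.

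**Conclusion.** The point holds in this form: PPV and NPV taken directly from this sample cannot be read as clinical predictive values, so they should not have primary standing as the objective is written. At the protocol's 80%/80% target, the permitted adult discovery numbers alone move PPV from 85.4% to 96.7% and NPV from 73.2% to 35.5%; the planned mix gives 94.1% and 50.0%.

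These figures assume that Se and Sp stay at 80% whatever the mix. The figures for acute versus recovery rest on an assumed share of patients with a recovery sample, and the 20% prevalence is illustrative. The protocol gives no intended-use prevalence, so the distance from any real clinical value cannot be stated.

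This is a defect in what is called primary and how it may be interpreted. It should be corrected, but it does not invalidate the recruitment plan or the sensitivity and specificity sizing.

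**What to change.** Change the synopsis, section 5.1 and section 10.1 together:

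1. Make sensitivity and specificity the primary accuracy measures, and name the comparator. Sections 10.1 and 21.3 currently use different ones, so this choice has to be made explicitly.
2. Move PPV and NPV to secondary. Compute them by Bayes' rule from the estimated sensitivity and specificity over a stated range of assumed intended-use prevalences (for example 20%, 50% and 80%), and say that this assumes both carry over to that setting.
3. If raw sample PPV or NPV are shown, print the sample case fraction beside them and do not present them as clinical values.

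The cost is a small wording amendment in three places, with whatever approval section 13.5 requires, and one extra table. No additional patients or measurements are needed, and the primary measures would then match those sized in section 21.3. PPV and NPV would lose their primary standing.

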The proposed program of research will identify and evaluate the diagnostic and prognostic value of exhaled breath metabolomic biomarkers in acute cardio respiratory breathlessness and common indicator diagnoses associated with acute cardio respiratory breathlessness. Specific indicator conditions have been selected according to their (i) relatively high prevalence, (ii) high unmet need, mortality and morbidity and (iii) need to develop better diagnostic and prognostic algorithms in acute care pathways.

The focus of the research program will be to phenotype using a combination of 'discovery' and near-patient care breath sampling technologies in acutely breathless patients attending two acute admissions units within Leicestershire. The indicator diagnoses of interest are (i) acute heart failure, (ii) exacerbations of adult asthma and COPD, (iii) community acquired pneumonia and (iv) paediatric exacerbations of acute childhood wheeze and confirmed asthma. Other disorders that are associated with acute breathlessness including exacerbations and acute presentations of pulmonary fibrosis, acute pulmonary embolism will not be studied within the program due to low prevalence, lack of standardised definitions and likely small sample size (pulmonary fibrosis) and adequate acute companion diagnostics (pulmonary embolism).

The program will be divided into two phases. **Phase 1**, a discovery phase to identify putative breath biomarker panels and **phase 2**, a validation phase to replicate and validate selected biomarkers within phase 1 using point of care breath sensing devices.

Patient level clinic-pathological and outcome data (spanning the entire acute pathway) will be collected in parallel to breath sampling. In addition, breath samples will be acquired during the recovery from the acute state and in the stable state post exacerbation to better understand the kinetics of breath analytes associated with these diseases.

A parallel cohort of age/home environment matched Adult/ parent/sibling/spousal healthy volunteers will also be recruited and evaluated at selected matching time points with breath analysis and a range of questionnaires to evaluate factors that are known to influence the metabolome including diet, lifestyle and the environment. Additionally patients with stable asthma, COPD and heart failure will be recruited from primary and secondary care as disease control populations.

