5.2 Secondary Objectives

- To replicate selected metabolomic breath biomarker panels of acute breathlessness using a combination of both (i) discovery technologies (including GC-MS) and (ii) point of care auto tuned breath sensing devices (including linear IMS, CMS, PTR-MS).
- To evaluate the primary endpoint stratified by breathlessness as follows (i) change in eMRC by 1
 unit, (ii) patient defined breathlessness and (iii) 100 mm visual analogue score for breathlessness
- To discover and replicate metabolomic breath biomarkers that differentiate (i) Acute Heart failure,
 (ii) Community acquired pneumonia, (iii) Adult exacerbations of asthma and COPD
- To quantify the level of clinical uncertainty in the primary diagnosis using a 100 mm visual analogue scale and independent clinical adjudication of case notes blinded to the following blood biomarkers (i) CRP (ii) blood eosinophils (iii) BNP (iv) Troponin-I but not clinical history and chest X-ray.
- To identify and discover metabolomic breath biomarkers of acute childhood wheeze and or confimed asthma.

To clinically validate metabolomic breath biomarkers generated above using a combination of existing pathology markers e.g. BNP, CRP, blood eosinophils and troponin- I and other clinical relevant prognostic scoring tools e.g DECAF, CURB65 and Heart failure risk calculator http://www.heartfailurerisk.org/^[19]

- Replication of acute breathlessness biomarkers will be according to the following predefined primary diagnoses in the replication phase:
 - (i) Acute Heart failure (n=55-100),(ii) Community acquired pneumonia (n=55-100), (iii) adult exacerbations of asthma and COPD (n=110-200),(iv) paediatric exacerbations of acute childhood wheeze and confirmed asthma (n=25-100),(v) age/home environment matched adult/spouse/sibling/parent control subjects (n=55-75 adults/25 children)
 - 5.3 Exploratory End Points (where applicable)
 - 1) To evaluate the dynamic profile of breath biomarkers during (i) the acute state, (ii) in the recovery state post exacerbation.

Page 15 of 46

- 2) To evaluate the relationship between breath metabolomic biomarkers and health status/ functional measures:
- Health status measures
- Physical performance
 - 3) To evaluate the relationship between metabolomic breath biomarkers and clinical outcomes including (i) hospital readmission at time points up to 2 years (ii) response to standard clinical therapy and (iii) death.

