10.7 Inclusion in Analysis

All eligible participants, that have provided informed consent and participated in either discovery or replication phase studies.

11.DIRECT ACCESS TO SOURCE DATA/DOCUMENTS

Direct access will be granted to authorised representatives from the sponsor, host institution and the regulatory authorities to permit trial-related monitoring, audits and inspections.

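### On any reading the primary accuracy estimate includes the patients used to find the markers, so it will be optimistic unless corrected; the planned replication cohort should supply it instead

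*Protocol*

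**What the plan says.** Section 5.1 gives the primary aim: "To evaluate the sensitivity, specificity, positive and negative predictive value of metabolomic biomarkers in exhaled breath samples to identify acute breathlessness". The bullet beneath it says that the acute group is recruited by "defined primary diagnoses in the discovery phase as defined by the treating physician" and lists discovery numbers only. The synopsis states the same objective with no phase attached.

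The first secondary objective in 5.2 is "To replicate selected metabolomic breath biomarker panels of acute breathlessness using a combination of both (i) discovery technologies", alongside point-of-care devices. GC-MS is named there as a discovery technology. Section 5.2 ends with its own list of replication numbers.

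Section 7.1 describes the first phase as "Phase 1: Discovery of novel breath metabolomic biomarkers". Section 4 describes the second as "a validation phase to replicate and validate selected biomarkers within phase 1 using point of care breath sensing devices".

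Section 10.1 models a two-level primary outcome, acute against recovery, by logistic regression and adds that "ROC curves will be produced for individual predictors in the primary analysis". It refers the detailed methods to a separate data analysis plan. Section 10.7 defines who is analysed: "All eligible participants, that have provided informed consent and participated in either discovery or replication phase studies". Section 21.4 claims 80% ± 8% sensitivity and specificity from 550 adults over both phases, and concedes that replication is adequately sized for sensitivity but not for specificity.

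**The concern.** Markers chosen because they separate the groups in one set of patients will separate those same patients better than new ones. The same holds for coefficients fitted and cut-offs chosen there. If accuracy is quoted on those patients without correction, it describes the fit to the sample and not the performance of the test. The primary result of this study is an accuracy claim, and Appendix C sets 80% sensitivity and specificity as the level of a useful marker. An inflated primary figure could make a weak panel look close to that level. The study already recruits an independent cohort that could give an unbiased answer, but that answer is ranked as secondary.

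**Working it through.** **1. Which patients can feed the primary estimate**

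| Place | Phase attached to primary accuracy |
|---|---|
| Synopsis | none stated |
| 5.1 | discovery list only |
| 5.2 | replication is secondary |
| 10.7 | either phase |
| 21.4 | 550 adults, both phases combined |

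There are two possible readings: discovery alone, or both phases pooled. Both contain the patients in whom markers are found. No section makes replication alone the source of the primary figure.

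**2. The plan's own precision figures (21.3)**

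N_sens = z² × 0.8 × 0.2 / (d² × prevalence) and N_spec = z² × 0.8 × 0.2 / (d² × (1 − prevalence)), with prevalence 0.8.

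- 95%, d = 0.05: 0.6147 / (0.0025 × 0.8) = 307.3 and 0.6147 / (0.0025 × 0.2) = 1,229.3. The plan has 307 and 1,230.
- 90% (z = 1.64), d = 0.05: 215.2 and 860.7. The plan has 215 and 861.
- 95%, d = 0.08: 120.05 and 480.2. The plan has 120 and 480.

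All reproduce. N_spec = 480 is covered only by the combined 550. It implies 480 × 0.2 = 96 healthy controls, against 55 to 75 adults planned in replication.

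**3. Half-widths at 80%, 1.96 × √(0.16/n), with healthy adults as the non-diseased group**

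| Set | Acute / healthy | Sensitivity | Specificity |
|---|---|---|---|
| Pooled, minimum | 440 / 110 | ±3.7 | ±7.5 |
| Discovery, minimum | 220 / 55 | ±5.3 | ±10.6 |
| Replication, minimum | 220 / 55 | ±5.3 | ±10.6 |
| Replication, upper range | 400 / 75 | ±3.9 | ±9.1 |

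The minimum counts come from 21.5 (four acute classes of 55, and 55 healthy, per phase).

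**4. Possible size of the optimism, with no true signal**

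Each setting has 300 simulated data sets of independent standard normal markers with no group difference. The 10 markers with the largest mean difference are combined in a linear score, and the AUC is computed in the same patients. The true AUC is 0.50. The 220 acute and 55 healthy are the discovery minimum. The 190 recovered, their independence from the acute samples, and the 100 and 300 candidates are assumptions.

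| Comparison | 10 markers, no selection | Best 10 of 100 | Best 10 of 300 |
|---|---|---|---|
| 220 acute v 190 recovered | 0.59 | 0.68 | 0.71 |
| 220 acute v 55 healthy | 0.63 | 0.76 | 0.80 |

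**5. With some true signal**

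Here five markers truly differ by 0.5 SD (assumed). A logistic score on the best 10 is cut at the Youden point, with 220 acute against 220 recovered treated as independent. The locked score and cut-off are then applied to a new sample of the same size.

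| Candidates | Apparent sensitivity / specificity | New sample |
|---|---|---|
| 10 | 0.73 / 0.73 | 0.70 / 0.70 |
| 100 | 0.74 / 0.75 | 0.69 / 0.69 |
| 500 | 0.75 / 0.76 | 0.68 / 0.68 |

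On the comparison in 10.1 the loss is about 3 to 8 points under these assumptions.

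**The case against.** The sentence in 5.1 is about recruitment. A reader might infer that it fixes the primary analysis set to discovery patients, but it does not. The link comes from its position under the primary objective and the parallel list in 5.2, and 10.7 leaves the phase open. This stands, but it changes only which of the two readings applies, and both include the selection patients.

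A reader might also infer that the plan prescribes selecting markers, choosing a cut-off and quoting uncorrected accuracy on the same people. The protocol says no such thing. Cross-validation or bootstrap correction may be in the data analysis plan, and their absence from the protocol is not a defect. So the claim must be conditional: optimistic unless corrected.

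Safeguards exist. Replication in new patients is planned, 10.2 calls the study exploratory, and it sets 20 events per model variable. That ratio limits overfitting of a fixed model but not the effect of screening many candidates. The unselected setting above, with 190/10 = 19 recovered samples per marker, gives 0.59; selection raises it to 0.68 to 0.71.

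Finally, the AUCs of 0.76 to 0.80 should not be read as the expected inflation of the primary analysis. They use healthy controls, whereas 10.1 compares acute with recovery. The only panel size in the document is 10 pre-specified aldehydes, used for sizing.

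**Conclusion.** The point holds in conditional form. The objectives and the analysis population place the primary accuracy in patients who include those used for marker selection. The independent cohort, which could answer the primary question without this bias, carries only a secondary objective. This is a design choice stated in the protocol and not a detail left to the analysis plan.

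The direction of the bias is certain if nothing corrects it; the size is not. It depends on the number of candidate compounds, their true effects and correlation, and the pairing of acute and recovery samples from the same patients. The protocol gives none of these in usable form, and the simulations ignore correlation and pairing.

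A reader might infer that moving to replication worsens specificity precision from ±7.5 to ±10.6 points. That is true only against the pooled reading; against discovery alone, precision at the planned minimum is unchanged. The change should be made, but a validation cohort is already planned, so it is a matter of which result is called primary.

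**What to change.** In 5.1, 5.2 and 10.1, state that the panel, coefficients and cut-off are locked on discovery data and that primary sensitivity, specificity and predictive values are estimated in replication patients. Specify the same discovery platform, GC-MS, which 5.2 already allows in replication. Make point-of-care performance secondary, because a locked cut-off cannot be assumed to carry over to another device. Label discovery or pooled accuracy exploratory, or report it only after an optimism correction that repeats the marker selection. Align 10.7 with this.

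The cost is more than wording: GC-MS samples must be analysed in enough replication patients. Where healthy controls are the non-diseased group, 21.4 should restate specificity precision as about ±10.6 points with 55 replication controls or ±9.1 with 75. Holding ±8 in replication alone would need about 96. If acute against recovery is the primary comparison, the precision should be restated for the expected number of recovery samples.
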